3.3 Pregnancy

The effects of DEBIRI on the developing human fetus at the recommended therapeutic dose are unknown. Women of child-bearing potential (WOCBP) and men must agree to use adequate contraception (hormonal or barrier method of birth control; abstinence) prior to study entry, for the duration of treatment, and for at least 3 months after the completion of treatment. Should a woman become pregnant or suspect she is pregnant while participating in this study, she must inform her treating physician immediately.

Prior to study enrollment, WOBCP must be advised of the importance of avoiding pregnancy during trial participation and the potential risk factors for an unintentional pregnancy. In addition, men enrolled on this study should understand the risks to any sexual partner of childbearing potential.

All WOCBP must have a negative pregnancy test within **72 hours** prior to receiving the first dose of the investigational agent(s). If the pregnancy test is positive, the patient must not receive protocol treatment and must not be enrolled in the study.

WOCBP is defined as follows: Any female who has experienced menarche and who has not undergone successful surgical sterilization (hysterectomy, bilateral tubal ligation, or a bilateral oophorectomy) or is not postmenopausal (defined as amenorrhea \geq 12 consecutive months, or women on hormone replacement therapy (HRT) with documented plasma follicle-stimulating hormone (FSH) level > 35 mIU/ml). Even women who are using oral, implanted, or injectable contraceptive hormones or mechanical products (diaphragm, condoms, spermicides) to prevent pregnancy or practicing abstinence or where partner is sterile (e.g. vasectomy), should be considered to be WOCBP.

3.4 Patient Registration

Eligible participants will be entered on study centrally by the Fox Chase Cancer Center QA Coordinator or their designee. Following registration, participants must begin protocol treatment within 14 days of registration. Issues that would cause treatment delays must be discussed with the Principal Investigator. If a participant does not receive protocol therapy following registration, the participant will be recorded as withdrawn from study. The Study Monitor must be notified as soon as possible if a participant does not begin protocol treatment as scheduled.

Participants may be registered from 9:00 am to 5:00 pm excluding holidays by calling the QA Coordinator at [contact]. The site's investigator or designee will then fax or email the completed registration form, consent and HIPAA signature pages and eligibility checklist to [contact]. The QA Coordinator or designee will notify the site by email once registration is confirmed and the sequence number has been assigned. Participants must be registered and have received a sequence number assigned by the QA Coordinator prior to the initiation of treatment.

4.0 Treatment plan

This will be a single-center phase I study of DEBIRI for the treatment of metastatic colorectal cancer with liver only or liver predominant metastases. Treatment will be given in the interventional radiology department. All patients will be hospitalized for observation following DEBIRI treatment. Reported adverse events and potential risks of these agents and appropriate dose modifications are described in Section 5.0. No investigational or commercial agents or therapies other than those described below may be administered with the intent to treat the patient's malignancy.

The following criteria for recovery of all toxicities must be documented prior to any additional DEBIRI treatments.

- Non-hematologic toxicities related to prior DEBIRI therapy must recover to \leq grade 1 prior to any additional treatment.
- Alkaline phosphatase/ AST/ALT level must recover to \leq grade 1 (less than 2.5 the upper limit of normal).
- Bilirubin elevation must recover to \leq grade 1 (less than 1.5 the upper limit of normal)
- Neutropenia and thrombocytopenia must recover to \leq grade 1 prior to any additional treatment

4.1 DEBIRI dose:

This will be a typical phase I study design of 3+3. The first cohort of patients will receive a dose of 50 mg of irinotecan per DEBIRI treatment. We will escalate by 25 mg with subsequent cohorts up to a dose of 100 mg of irinotecan per DEBIRI treatment (section 4.3).

Table 2: Dose Escalation Schedule

Dose Level	Dose of Irinotecan in beads
Level 1	50 mg per dose
Level 2	75 mg per dose
Level 3	100 mg per dose

At each dose level patients will be treated based on the presence of unilobar or bilobar disease and treated as described below.

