3.0 Patient selection

3.1 Inclusion

3.1.1 Patients must be 18 years or older.

3.1.2 Patients must have a histologically or cytologically confirmed adenocarcinoma of the colon or rectum that is metastatic to the liver and unresectable and for which standard curative measures do not exist or are no longer effective.

3.1.3 Patients must have received prior fluoropyrimidine, oxaliplatin and irinotecan-based therapy for their disease and had progression or intolerance to these agents that resulted in treatment discontinuation.

3.1.4 Liver disease must not be amenable to potentially curative surgical resection.

3.1.5 Patients must have liver-only or liver-predominant disease to be eligible for this study. Liver predominant disease is defined dominant metastatic burden in the liver, with extra-hepatic disease that is judged by the investigator as unlikely to be life threatening within 3 months.

3.1.6 Patients must have a patent portal vein as documented by CT, MRI, or ultrasound.

3.1.7 Prior radiation therapy is allowed but must have been completed ≥ 4 weeks prior to study entry. Patients with history of prior radiation to the liver including radio-labeled microspheres cannot take part in this study.

3.1.8 Eastern Cooperative Oncology Group performance status 0 or 1.

3.1.9 Previous surgery or RFA to the liver is allowed. Patients with history of chemoembolization or radio-labeled microspheres are excluded.

3.1.10 Life expectancy of ≥ 12 weeks.

3.1.11 Patients must have organ and marrow function as defined below:

Leukocytes	$\geq 3,000/\mu\text{L}$
Absolute Neutrophil Count	$\geq 1,500/\mu\text{L}$
Platelets	$\geq 100,000/\mu\text{L}$
Total Bilirubin	$\leq 1.5 \times \text{ULN}$
AST(SGOT)/ALT(SGPT)	$\leq 2 \times \text{ULN}$
Alkaline Phosphatase	$\leq 2 \times \text{ULN}$
Creatinine	$\leq 2.0 \times \text{mg/dL}$
PT/PTT	$\leq 1.5 \times \text{ULN}$

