4.1.1 Patients with unilobar disease

At each dose level the involved lobe will be treated twice with the appropriate dose of DEBIRI once every 3 weeks. CT scan for evaluation of response will be performed at 8 weeks. Further treatment is at the discretion of the treating physician.

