4.1.2 Patients with bi-lobar disease

At each dose level the dominant lobe will be treated with the appropriate dose of DEBIRI for two treatments 3 weeks apart. CT images of the liver will be used to determine which lobe has the highest number or the largest lesions, and will be considered the dominant lobe. The response will be evaluated with CT at 8 weeks. In the absence of evidence of progression in the treated lobe (dominant lobe), 2 additional treatments can be administered to the untreated (non-dominant) lobe, at the same dose level. Repeat CT scan will be performed at 16 weeks. Further treatment is at the discretion of the treating physician.

- Treatment considerations
- Prior to each subsequent therapy patients will have all their blood work reviewed, to assure that they fill the eligibility criteria set forth for the study in section 3.1.11.
- Treatment may be delayed up to 2 additional weeks for labs to recover
- Failure to recover after 2 additional weeks will result in patient removal from the study
- Evaluating Response
- For purposes of planning follow-up treatments and measuring response, response will be defined by RECIST criteria for the treated lobe only.

- Progression of extra-hepatic metastases or progression in the untreated lobe will not be considered progression for the purposes of this trial. However, in these cases the patient and his treating physician may elect to terminate participation in this study.
- Response rate in treated liver lesion will be classified using RECIST criteria as outlined in section 8.0.

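### Sections 4.0 and 4.1.2 set different ALP/AST/ALT limits for repeat DEBIRI treatment (below 2.5 × ULN against at most 2 × ULN), and the delay and removal rule does not say which one it uses

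*Combined protocol and SAP*

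**What the plan says.** Three places in the protocol bear on whether a patient may be treated again.

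- **Section 4.0** lists recovery criteria that "must be documented prior to any additional DEBIRI treatments". For alkaline phosphatase, AST and ALT the criterion is "grade 1 (less than 2.5 the upper limit of normal". The list applies to every patient and sets no time limit.
- **Section 4.1.2**, in the bullets on treatment considerations, has blood work reviewed before each later treatment "to assure that they fill the eligibility criteria set forth for the study in section 3.1.11". It continues: "Treatment may be delayed up to 2 additional weeks for labs to recover", and then "Failure to recover after 2 additional weeks will result in patient removal from the study".
- **Section 3.1.11**, introduced by "Patients must have organ and marrow function as defined below", is the table to which 4.1.2 refers. Its rows for alkaline phosphatase and for AST/ALT each give an upper limit of 2 × ULN.

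Section 4.1.1, for unilobar disease, says that "the involved lobe will be treated twice with the appropriate dose of DEBIRI once every 3 weeks". It contains no laboratory check, delay limit or removal rule of its own and does not refer to those in 4.1.2.

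**The concern.** Two sections give different numbers for the same decision on the same three analytes, and neither mentions the other. A patient at, say, 2.25 × ULN on the day of the second treatment has recovered according to 4.0 and fails the check in 4.1.2.

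The removal rule adds to the difficulty because it turns on whether labs recover. Its position directly after the reference to 3.1.11 suggests the limit of 2 × ULN. But section 4.0 is the place that attaches a number to recovery, and that number is 2.5. Two investigators could read the rule differently, each with some support in the text.

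At stake is who receives a second treatment, and when. Section 4.3 counts dose-limiting toxicities (DLTs) in the three weeks after each treatment, so the same limit also decides who enters a second observation period.

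**Working it through.** The plan gives no figure to reproduce. The check compares the two rules directly.

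**Inputs.** Section 4.0: value < 2.5 × ULN. Section 3.1.11, through 4.1.2: value ≤ 2 × ULN. Delay: up to 2 weeks (4.1.2). Second treatment: Day 22, within 2 days either way (section 7.0).

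**Step 1. Apply both rules to a range of values.**

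| ALP, AST or ALT (× ULN) | Section 4.0 | 3.1.11 through 4.1.2 |
|---|---|---|
| 1.9 | met | met |
| 2.0 | met | met |
| 2.01 | met | not met |
| 2.25 | met | not met |
| 2.49 | met | not met |
| 2.5 | not met | not met |
| 2.6 | not met | not met |

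The rules differ only above 2.0 and below 2.5 × ULN, a band of 2.5 − 2.0 = 0.5 × ULN. Bilirubin does not raise the same problem: 4.0 has < 1.5 × ULN and 3.1.11 has ≤ 1.5 × ULN, so they differ only at exactly 1.5.

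**Step 2. Suppose both rules apply.** A value must be < 2.5 and ≤ 2.0, which reduces to ≤ 2.0. The 2.5 figure then never changes a decision.

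**Step 3. Follow a value that stays in the band, for example 2.25 × ULN.**

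- Only 4.0 applies: treated on schedule at Day 22.
- Both apply, and recovery in the removal rule means ≤ 2.0: delayed to at most Day 22 + 14 = Day 36, then removed. If the value falls to 2.0 or less in that time, treatment can follow by Day 36.
- Both apply, but recovery means < 2.5: the patient fails the check for treatment yet has recovered for the removal rule, so is neither treated nor removed. The text does not provide for this case.

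**Step 4. Scope.** If the bullets in 4.1.2 cover bilobar patients only, unilobar patients face only the 2.5 limit, with no time limit. If the bullets cover everyone, Steps 2 and 3 apply to all.

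**Step 5. Number of patients.** Section 1.3 cites a phase III study in which 58% of DEBIRI patients had liver tests above 3 × ULN. It adds that all values had normalized by three weeks, with no treatment delays. That gives no count of patients between 2.0 and 2.5 × ULN at Day 22, and no other section does.

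**The case against.** The strongest reply is that this is not a logical contradiction. Both rules are necessary conditions, and such conditions accumulate. Any value at or below 2 × ULN satisfies both, and where both apply the stricter one governs. The lists also serve partly different purposes: 4.0 covers clinical toxicities, while 3.1.11 adds items such as creatinine and PT/PTT. This stands, and it is the natural reading for a bilobar patient. It leaves open why 4.0 carries a number with no effect, and which number the removal rule uses.

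On scope, the documents lean towards study-wide application. The bullets speak of patients and later treatments without a bilobar qualifier. The neighbouring bullets on response restate rules that hold for the whole study. Section 7.0 gives a single timetable for unilobar and bilobar disease, with chemistry before treatment and coagulation tests before each procedure. The list levels may also have been lost when the PDF was read. So this is a point to confirm, and it would go too far to say that unilobar patients are exempt.

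A reader might also infer more than the documents support:

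- **That the MTD is compromised because a removed patient loses half of the DLT observation.** Such a patient would have one of two three-week periods, but that is arithmetic and shows no effect on the MTD. The DLT definition is the same under either limit. Whether the patient still counts depends on the undefined term cycle in section 9.0, which is a separate matter.
- **That the centre's earlier experience shows many patients in the band.** Sections 1.4 and 1.5 describe raised alkaline phosphatase, but the available text does not place values between 2.0 and 2.5 × ULN.
- **That the pointer in 4.0, "appropriate dose modifications are described in Section 5.0", is part of this conflict.** Section 5.0 deals with adverse event definitions and reporting, so the pointer does not help here. But it concerns dose modification, and is a separate cross-reference to correct.

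**Conclusion.** The inconsistency is real and limited. For alkaline phosphatase, AST or ALT above 2.0 and below 2.5 × ULN, section 4.0 and section 4.1.2 (through 3.1.11) give different answers about repeat treatment. No text gives one precedence or ties the removal rule to a number. For a patient in that band the second treatment may come at Day 22, as late as Day 36 (each within the calendar's tolerance), or never.

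This rests on the wording alone and on no assumption about event rates. That the bullets cover all patients is probable but not certain. The number of patients affected, and any effect on the MTD, cannot be estimated from the documents. No view is taken on which limit is clinically right.

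**What to change.** Reconcile sections 3.1.11, 4.0 and 4.1.2 by amendment:

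1. State one limit for alkaline phosphatase, AST and ALT that governs repeat treatment, chosen by the clinical team, and use it wherever repeat treatment is described.
2. Tie the delay and removal rule to that limit explicitly, so that recovery has one meaning.
3. State whether the delay and removal rule covers all patients or bilobar patients only. If all, move the bullets out from under the bi-lobar heading.

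The cost is a change of wording. No tests are added, because footnote c of the study calendar already requires chemistry before each treatment and weekly on study.

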4.1.1 Patients with unilobar disease

At each dose level the involved lobe will be treated twice with the appropriate dose of DEBIRI once every 3 weeks. CT scan for evaluation of response will be performed at 8 weeks. Further treatment is at the discretion of the treating physician.

4.1.2 Patients with bi-lobar disease

At each dose level the dominant lobe will be treated with the appropriate dose of DEBIRI for two treatments 3 weeks apart. CT images of the liver will be used to determine which lobe has the highest number or the largest lesions, and will be considered the dominant lobe. The response will be evaluated with CT at 8 weeks. In the absence of evidence of progression in the treated lobe (dominant lobe), 2 additional treatments can be administered to the untreated (non-dominant) lobe, at the same dose level. Repeat CT scan will be performed at 16 weeks. Further treatment is at the discretion of the treating physician.

- Treatment considerations
- Prior to each subsequent therapy patients will have all their blood work reviewed, to assure that they fill the eligibility criteria set forth for the study in section 3.1.11.
- Treatment may be delayed up to 2 additional weeks for labs to recover
- Failure to recover after 2 additional weeks will result in patient removal from the study
- Evaluating Response
- For purposes of planning follow-up treatments and measuring response, response will be defined by RECIST criteria for the treated lobe only.

- Progression of extra-hepatic metastases or progression in the untreated lobe will not be considered progression for the purposes of this trial. However, in these cases the patient and his treating physician may elect to terminate participation in this study.
- Response rate in treated liver lesion will be classified using RECIST criteria as outlined in section 8.0.

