7.0 Study Calendar

All pre-study/baseline evaluations except serum pregnancy test may be performed up to 28 days prior to registration. A timetable of relevant assessments is provided in the table below for uni-lobar and bi-lobar disease (all tests can be performed within ± 2 days of this schedule). This timetable contains the schedule for two treatments 3 weeks apart followed by CT on week 8. The schedule can be repeated for additional treatment in appropriate cases (section 4.2.1).

Based on experience from previous studies using DEBIRI there exists a risk of post procedure transient edema, which may confound the response evaluation by RECIST criteria. In case of disease progression on week 8 imaging the patient will be followed with repeat CT at 12 weeks to rule out the possibility of edema accounting for the progressive disease.

Study Calendar

	Pre-Study	Day 1 (± 2) ⁱ	Day 2 ⁱ	Day 8	Day 15	Day 22 (± 2) ⁱ	Day 23 ⁱ	Day 29	Day 36	Day 57	EOT ^h	Follow Up for Survival ^j
Planned treatment (Unilobar/dominant lesion in bilobar disease) ± 2 days ^a		X				X						
Informed consent	X											
Demographics	X											
Medical History ^b	X											
Concurrent meds	X	X-----X										
Physical exam ^b	X		X	X	X	X	X	X	X		X	
Height	X											
Performance Status	X					X					X	
CBC w/diff ^c	X		X	X	X	X	X	X	X		X	
Serum chemistry ^c	X		X	X	X	X	X	X	X		X	
CEA ^d	X									X	X	
PT/INR/PTT ^e	X					X					X	
Adverse Event Evaluations		X-----X										
CT scan of the chest abdomen & pelvis ^f	X									X ^K		
B-HCG ^g	X											
Hepatic angiogram		X										

a. Patients with unilobar disease will be treated on day 1 ± 2 days and 3 weeks later on day 22 ± 2 days with CT 8 weeks after the initial treatment. Patient with bilobar disease will receive treatment to the dominant lobe on day 1 ± 2 days and 3 weeks later on day 21 ± 2 days with CT 8 weeks after the initial treatment. Patients without evidence of progression will be candidates for treatment of the non-treated lobe for 2 treatments 3 weeks apart.
b. Medical history and physical examination will be obtained prior to each treatment according to the treatment schedule (± 2 days). Pre-treatment medical history can consist of interval history.
c. CBC and Chemistry are to be obtained on the day before treatment (± 2 days), and every week while on the study (± 2 days). Additional blood tests should be performed per the discretion of the treating physician. Blood work obtained within ± 2 days may be used.

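### Section 4.1.2 pins the second-lobe CT to study week 16, which equals the plan's 8-week evaluation only if that lobe is first treated on about day 57

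*Combined protocol and SAP*

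**What the plan says.** In bilobar disease the dominant lobe is treated twice, 3 weeks apart, and scanned at week 8. Section 4.1.2 then opens the second lobe: "In the absence of evidence of progression in the treated lobe (dominant lobe), 2 additional treatments can be administered". Of the scan that follows it says only "Repeat CT scan will be performed at 16 weeks". Footnote a in section 7.0 repeats the gate ("Patients without evidence of progression will be candidates for treatment of the non-treated lobe for 2 treatments 3 weeks apart"), but it ties the first-course scan to treatment: "CT 8 weeks after the initial treatment". Section 8.0 likewise sets response evaluation at 8 weeks after DEBIRI for every patient. Section 7.0 allows the two-treatments-plus-CT calendar to be run again for further treatment, citing a section 4.2.1 that does not appear in the text.

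Section 4.1.2 also foresees late treatment: "Prior to each subsequent therapy patients will have all their blood work reviewed", and "Treatment may be delayed up to 2 additional weeks for labs to recover".

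Section 7.0 warns that transient edema after the procedure may confound RECIST. It, section 8.0 and footnote k call for a repeat CT at week 12 when the week-8 scan shows progression. Footnote k names the Day 57 scan. Section 4.6 ends therapy on progression in the treated lobe and does not mention the week-12 CT.

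**The concern.** One scan is timed from treatment and the other by study week. The two rules agree when nothing slips. When the second lobe starts late, which the plan expressly allows, the week-16 scan does not move, so that lobe is read earlier than the first lobe was.

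At stake are the response rate and time to progression in treated liver, both secondary objectives. The plan regards edema as a possible source of apparent progression on a scan 35 days after the last treatment. A scan closer to the last treatment is more exposed if edema subsides with time, which is what the week-12 repeat CT presumes. No re-check is stated for the second-lobe scan.

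**Working it through.** **Inputs**
- First course (section 7.0): treatments on days 1 and 22, CT on day 57.
- Second course (4.1.2, footnote a): two treatments 3 weeks apart; CT at week 16. No origin is given for week 16. I count from first treatment, as footnote a does for week 8, so the CT is on day 1 + 16 × 7 = 113.
- Laboratory delay before a treatment (4.1.2): d, from 0 to 14 days.
- Lag from the week-8 scan to treatment 3 (T3): k days. The text gives no day for T3. I take k = 0 as the base case, the most favourable to the plan, and show k = 7 as a range.

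**Formulas**
- T3 = 57 + d + k; T4 = T3 + 21.
- CT on day 113: days from the lobe's first treatment = 113 − T3 = 56 − d − k; days from its last = 113 − T4 = 35 − d − k.
- CT timed from treatment: day T3 + 56, always 56 days from the first treatment and 56 − 21 = 35 from the last.

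**The plan's own figure.** The first course gives 57 − 1 = 56 and 57 − 22 = 35 days. With d = k = 0, T3 and T4 fall on days 57 and 78, and 113 − 57 = 56, 113 − 78 = 35. Week 16 is therefore reproduced for an on-time start.

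**Later starts**

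| Case | T3 / T4 (day) | CT on day 113: days from first / last | Day of CT if timed from T3 |
|---|---|---|---|
| No delay | 57 / 78 | 56 / 35 | 113 |
| 7-day lag | 64 / 85 | 49 / 28 | 120 |
| 14-day lab delay | 71 / 92 | 42 / 21 | 127 |
| 14-day lab delay and 7-day lag | 78 / 99 | 35 / 14 | 134 |

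For the 14-day lab delay, section 4.1.2 and a repeated section 7.0 calendar differ by 127 − 113 = 14 days.

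**Delay before T4 only.** T4 = 78 + 14 = 92 and 113 − 92 = 21 days. Timing the scan from T3 leaves it on day 113, so nothing changes. The first course behaves the same way: T2 on day 22 + 14 = 36, and 57 − 36 = 21. The discrepancy therefore comes from a late T3.

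**The gates.** Sections 4.1.2, 4.6 and footnote a turn on progression in the treated lobe and do not name the week-12 CT. Sections 7.0, 8.0 and footnote k require that CT after week-8 progression, but do not say that the second-lobe decision waits for it.

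**The case against.** The best reply is that week 16 is simply the nominal 8 + 8 date. Section 8.0 already sets 8 weeks after DEBIRI, and section 7.0 lets the calendar be repeated, so a late start would carry the scan, and arguably its edema re-check, along with it. This is a sensible reading and may be what was intended. But 4.1.2 governs bilobar treatment and fixes a week, nothing says which section prevails, and footnote k ties the re-check to Day 57.

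Second, a late treatment 2 in the first course also leaves only 21 days after the last treatment. That stands, but the first-course scan has a stated re-check and the second-lobe scan does not. Section 8.0's confirmation of responses at least 4 weeks later guards against an early false response, not against edema read as progression. Footnote f permits extra imaging but does not require it.

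Third, the treatment schema is a figure missing from the text available here. It might give a day for treatment 3, so my statement that none is given covers the text only.

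Two stronger readings are tempting:
- A reader might infer that a patient cleared of edema at week 12 starts the second lobe on day 85 and is scanned on day 113, 28 days after its first treatment and 7 after its last, or even before a delayed treatment 4. That combines a flexible gate with a rigid scan date. Read literally throughout, no week-12 course exists. Read by purpose throughout, the scan moves to day 85 + 56 = 141, at 56 and 35 days.
- A reader might infer that the plan denies the second lobe to a patient whose week-8 enlargement was edema. Sections 7.0 and 8.0 imply that such progression is provisional, and 4.1.2 sends the reader to 8.0 ("Response rate in treated liver lesion will be classified using RECIST criteria as outlined in section 8.0"). The gap is that the gates do not say so.

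**Conclusion.** The concern holds as a minor inconsistency in scan timing. The fixed week-16 CT conflicts with the plan's 8-week rule whenever treatment 3 falls later than about day 57 (the calendar allows ±2 days). At the full laboratory delay, and with no other lag, the second lobe is read 14 days early: 42 and 21 days from its first and last treatments instead of 56 and 35. No edema is needed for this case to arise. The gate wording calls for clarification and is not a separate flaw.

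This rests on counting week 16 from first treatment and on giving treatment 3 no earlier than the week-8 scan that permits it. Any lag after that scan makes the intervals shorter. The MTD and DLT rules do not depend on this scan. Planned accrual is 9–30; the bilobar share and the frequencies of laboratory delay and edema are not given, so the number affected cannot be stated and is likely small.

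**What to change.** In 4.1.2, replace the week-16 date with: *8 weeks after the first treatment of the non-dominant lobe (nominally week 16)*. Add that progression on that scan is re-checked by CT 4 weeks later, as for the first lobe: day 113 + 28 = 141 nominally, or 127 + 28 = 155 after a full laboratory delay.

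As a consistency edit, state in 4.1.2, footnote a and 4.6 that treated-lobe progression at week 8 is provisional until the week-12 CT, and that a patient cleared then may go on to the second lobe. Whether to wait in a given patient remains a clinical decision. The section 4.2.1 reference in 7.0 can be corrected at the same time. A line in 8.3 dating confirmed progression to the first scan would be a clarification only, in keeping with 8.2.

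The cost is a few sentences, a somewhat later CT for bilobar patients who start the second lobe late (day 127 instead of 113 at the full delay), an occasional repeat scan, and up to 4 weeks' wait for some patients who prove to have true progression. The nominal schedule does not change.
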